## 6. Study Treatment

NT-I7 and Pembrolizumab

### 6.1. Study Treatment Administration

Reported AE and potential risks are described in Section 11.1. Appropriate dose modifications are described in Section 8.1 and 8.2. No investigational or commercial agents or therapies other than those described below may be administered with the intent to treat the subject's malignancy.

Treatment will be administered on an outpatient basis.

**Table 2: Study treatment details**

Study Treatment	Dosage Formulation	Unit Dose Strength	Dosage Level(s)	Route	Regimen or Treatment Period	Sourcing
NT-I7	Solution for injection	25 mg/mL	Dose in $\mu\text{g}/\text{kg}^a$ Q6W	IM injection	Day 1 of alternate cycle	Provided centrally by Sponsor
Pembrolizumab (MK-3475)	Solution for infusion	100 mg/vial	200 mg Q3W	IV infusion	Day 1 of every cycle	Provided centrally by Sponsor

Abbreviations: IM=intramuscular; IV=intravenous.

aRefer to Sections 5.4, 5.5 and 5.6 for assigned dose level.

#### 6.1.1. NT-I7

Chemical Formula:  $\text{C}_{4012}\text{H}_{6350}\text{N}_{1104}\text{O}_{1238}\text{S}_{42}$

Structural Formula: NT-I7 is a fusion protein comprising human IL-7 fused to the human IgD hinge region. This in turn is fused to the N-terminal region of CH2 from IgD and two key regions of the antibody IgG4: C-terminal region of CH2 and the entire CH3 region.

##### 6.1.1.1. NT-I7 Pharmaceutical Information

NT-I7 protein is produced by inserting the gene expressing rhIL-7-hyFc into the eukaryotic expression vector pAD15 at the Multiple Cloning Site. The CHO cell line DG44 is used to produce NT-I7. NT-I7 has a molecular weight of 104 KDa and is composed of 400 amino acids with 155 amino acids for IL-7 and 30 for the IgD hinge, 8 for IgD the CH2 domain, and 207 for the IgG4 region. NT-I7 contains 11 disulfide bonds, 1 O-glycosylation and 3 N-glycosylation sites.

**Pharmaceutical Properties:** NT-I7 is supplied in a sterile, preservative-free liquid form in a single-use vial. One vial (1.0 mL) contains 25 mg per 1 mL of the active ingredient of the finished drug product. The purity of the active ingredient must be 89.0% or higher based on size-exclusion ultra-high-performance liquid chromatography (SE-UHPLC) testing and 90.0% or

higher based on reverse-phase high-performance liquid chromatography (RP-HPLC) testing. The NT-I7 finished drug product should be a colorless, clear solution and should not contain any particulate matter that can be observed visually.

**Dosage Form:** In addition to the active ingredient NT-I7, each vial contains sucrose, D-sorbitol, tri-sodium citrate dehydrates, citric acid monohydrate and Polysorbate 80 as a stabilizer and buffer. These ingredients meet the specification criteria of the European pharmacopeia (Ph. EUR). NT-I7 is supplied in a 1.0 mL vial package at a concentration of 25 mg protein/mL. The finished drug product solution contained in the vial is a liquid injection dosage form at pH  $5.0 \pm 0.5$  and a colorless, clear solution. There should not be any floating particulates under gross observation. For information on the injection sites, please refer to *NT-I7 Pharmacy Manual*.

**Storage and Handling of NT-I7:** Vials that contain NT-I7 must be kept refrigerated at 2~8°C. NT-I7 vials should NEVER BE FROZEN. It is recommended that vials are protected from direct light until the time of use.

**Route of Administration:** IM injection. DO NOT SHAKE vials before injection. A vial is restricted to 1 subject and to 1 day of treatment.

#### 6.1.1.2. NT-I7 Dosing

Subjects will receive NT-I7 according to the following dose escalation schedule. Dose escalation will proceed within each dose level as described in Section 5.3.

The NT-I7 dose will be administered 45 ( $\pm 15$ ) minutes after Pembrolizumab on all days where concurrent administration is planned. NT-I7 dose administered will be determined using the subject's body weight. Refer to the *NT-I7 Pharmacy Manual* for details.

NT-I7 will be injected intramuscularly. Guidelines for IM injection by the research nurse or investigator are described in the *NT-I7 Pharmacy Manual*.

On the odd-numbered cycles as pembrolizumab and NT-I7 are administered, vital signs need to be obtained within 60 minutes prior to the start of the pembrolizumab infusion and repeated after the completion of the infusion but before the NT-I7 injection.

#### 6.1.2. Pembrolizumab

Pembrolizumab will be administered using IV infusion on Day 1 of each 3-week treatment cycle after all procedures and assessments have been completed. [*NT-I7 to be administered 30-60 minutes post administration of pembrolizumab on days where concurrent administration is planned*].

Pembrolizumab will be administered as a dose of 200 mg using a 30-minute IV infusion. Sites should make every effort to target infusion timing to be as close to 30 minutes as possible. However, given the variability of infusion pumps from site to site, a window between -5 minutes and +10 minutes is permitted (i.e., infusion time is 30 minutes (-5 min/+10 min)).

On the even-numbered cycles (only pembrolizumab administered), vital signs need to be obtained within 60 minutes prior to the start of the pembrolizumab infusion.

*The Pembrolizumab Pharmacy Manual contains specific instructions for the preparation of the pembrolizumab infusion and administration of infusion solution.*

## 6.2. Dose-Limiting Toxicity

All toxicities will be graded using NCI CTCAE Version 5.0. For the purpose of this study, a DLT is any event attributed to NT-I7 and/or to pembrolizumab and occurring during the DLT period of first 21 days.

Dose-limiting toxicity is defined as any AE occurring within the first 21 days (i.e., Cycle 1, Day 1 through Day 21), that is considered to be at least possibly, probably, or definitely related to the study treatment (NT-I7 and/or pembrolizumab) per the investigator, and that meets at least one of the non-hematologic or hematologic criteria listed below.

### 6.2.1. DLT criteria

1. Grade 4 non-hematologic toxicity (not laboratory).
2. Grade  $\geq 3$  diarrhea, nausea, or vomiting without use of anti-emetics or anti-diarrheals per standard of care
3. Grade  $\geq 3$  rash lasting  $\geq 5$  days
4. Grade 4 neutropenia lasting  $\geq 5$  days
5. Febrile neutropenia Grade 3 or Grade 4:
  - Grade 3 is defined as  $ANC < 1000/\text{mm}^3$  with a single temperature of  $> 38.3$  degrees C (101 degrees F) or a sustained temperature of  $\geq 38$  degrees C (100.4 degrees F) for more than 1 hour
  - Grade 4 is defined as  $ANC < 1000/\text{mm}^3$  with a single temperature of  $> 38.3$  degrees C (101 degrees F) or a sustained temperature of  $\geq 38$  degrees C (100.4 degrees F) for more than 1 hour, with life-threatening consequences and urgent intervention indicated.
6. Other Grade 4 hematologic toxicity lasting  $\geq 7$  days, except thrombocytopenia:
  - Grade 4 thrombocytopenia of any duration
  - Grade 3 thrombocytopenia associated with clinically significant bleeding

**Note:** Peripheral lymphocytopenia after the first NT-I7 injection is not a sign of toxicity; it reflects the lymphocytes “homing effect” of NT-I7. Lymphocyte counts usually come back to baseline 5 to 7 days after the first injection.

7. Any non-hematologic AE  $\geq$  Grade 3 in severity should be considered a DLT, with the following exception: Grade 3 fatigue lasting  $\leq 3$  days.; without use of corticosteroids or anti-inflammatory agents per standard of care.
8. Any Grade 3 or Grade 4 non-hematologic laboratory value if:
  - Clinically significant medical intervention is required to treat the subject, or
  - The abnormality leads to hospitalization, or
  - The abnormality persists for  $> 1$  week, or

- The abnormality results in potential Drug-induced Liver Injury (DILI) as defined by Hy's Law.  
Exceptions: Clinically nonsignificant, treatable, or reversible laboratory abnormalities including liver function tests, uric acid, etc.
- 9. Other Grade  $\geq 3$  clinical laboratory abnormalities must be reversible to  $\leq$  Grade 1 within 72 hours with outpatient care and/or monitoring AND must not be considered clinically significant by the treating physician to be excluded from the definition of DLT.
- 10. Prolonged delay ( $> 2$  weeks) in initiating Cycle 2 due to treatment-related toxicity.
- 11. Any treatment-related toxicity that causes the subject to discontinue treatment during Cycle 1.
- 12. Grade 5 toxicity.

Once all subjects in a dose level have completed the 3-week (21 days) DLT window, the AEs will be assessed by the DMC, which includes the Protocol PI, Study Medical Monitor, Study Statistician, and Study Sponsor's designee.

The subjects must complete the full 3-week DLT window to be considered evaluable for DLTs. Subjects who discontinue from the study before completion of the full 3-week DLT window for reasons other than the occurrence of a DLT (e.g., withdrawal of consent, rapid tumor progression, death due to rapid tumor progression, AE that does not meet DLT criteria) will not be considered evaluable for DLTs and will be replaced.

All subjects will be monitored for occurrence of DLT. Monitoring of all safety and toxicity data is done by the PIs, the study Sponsor and/or designee on a real-time basis as data are entered into the electronic data capture (EDC) system. All participating sites must notify the protocol PI and the Sponsor or designee when a DLT has occurred.

### **6.3. Subject Replacement**

Subjects who receive at least 1 dose of the investigational treatment will be considered evaluable for safety and included in the overall safety analysis.

Subjects who discontinue from the study before completion of the full 3-week DLT window for reasons other than the occurrence of a DLT (e.g., withdrawal of consent, rapid tumor progression, death due to rapid tumor progression, AE that does not meet DLT criteria) will not be considered evaluable for DLTs and will be replaced.

### **6.4. Discontinuation of Study Intervention, Subject Discontinuation/Withdrawal, and Study Termination**

#### **6.4.1. Discontinuation of Study Intervention**

In the absence of treatment delays due to AE(s), treatment with NT-I7 and pembrolizumab may continue for approximately 2 years or up to 35 cycles of study treatment relative to the date of the 1st dosing or until one of the following criteria applies:

- Disease progression warranting alternative systemic therapy

## V7.0 incorporating Amendment 6, 26Oct2023

**Note:** Subjects with RECIST-defined progressive disease (PD) who are otherwise stable without symptomatic progression should continue study treatment until the next radiographic imaging time point (at least 4 weeks after the prior assessment of PD) to assess for possible pseudo-progression.

Discontinuation from treatment does not represent withdrawal from the trial.

Subjects may discontinue treatment at any time for any reason or be dropped from treatment at the discretion of the Investigator, should any untoward effect occur. In addition, a subject may be discontinued from treatment by the Investigator or the Sponsor, if treatment is inappropriate, the trial plan is violated, or for administrative and/or other safety reasons.

A subject may be discontinued from treatment but continue to be monitored in the trial for any of the following reasons:

- The subject or subject's legally acceptable representative requests to discontinue treatment
- The Investigator believes that for safety reasons or tolerability reasons (e.g., AE) it is in the best interest of the subject to discontinue study drug.
- Intercurrent illness that prevents further administration of treatment
- Unacceptable AEs (e.g., those meet the DLT criteria or other adverse events which can jeopardize patient safety per enrolling physician or considered unacceptable by the subject)
- Progressive disease confirmed radiographically.
  - *Note: In the case of suspected pseudoprogression, patients will be advised to continue treatment beyond initial RECIST 1.1-defined PD while waiting for confirmation of PD, provided they are clinically stable (per iRECIST). Investigators are recommended to consult with the Sponsor designee regarding individual cases.*
  - Treatment interruption lasting >12 weeks (see Section [8.1.1](#))
  - The patient becomes pregnant. Refer to Section [11.8](#).
  - Noncompliance with study procedure requirements or study drug administration (e.g., non-compliance with study visits and miss too many drug administrations).
  - The subject persistently uses a disallowed medication as discussed with the Sponsor's designee.
  - Discontinuation of treatment may be considered, at the discretion of the treating physician per criteria below, but continue to be monitored in the study for any of the following reasons:
    - Recurrent Grade 2 pneumonitis
    - Discontinuation of treatment may be considered for subjects who have attained a confirmed complete response (CR) and have been treated for at least 8 cycles (at least 24 weeks), receiving 2 cycles of the combination including 2 doses of pembrolizumab and had at least 2 treatments of NT-I7 beyond the date when the initial CR was declared. Completion of up to 35 treatments (or approximately 2 years) with pembrolizumab. *Note: The number of administrations is calculated starting with the first dose of pembrolizumab.*

- Any study intervention-related toxicity specified as a reason for permanent discontinuation as defined in the guidelines for dose modification due to AEs in Section 8.2.

The reason(s) for protocol treatment discontinuation, the reason(s) for study removal and the corresponding dates must be documented in the CRF.

If a subject discontinues study drug for any reason (except withdrawal of consent from the study), end of treatment/early withdrawal assessments should be obtained as soon as possible and follow up assessments should be obtained according to SOA. Subjects who permanently discontinue study treatment for reasons other than objective RECIST 1.1 and iRECIST disease progression should continue to have scans performed as scheduled, at the investigative site or locally, up to one year after discontinuation of study treatment. Standard of care disease assessments will be collected until the start of a new anticancer treatment, disease progression, pregnancy, death, withdrawal of consent or end of study, whichever occurs first.

Subjects removed from study for unacceptable AE(s) will be followed until resolution or stabilization of the AE; in addition, the subjects will be followed for disease status and overall survival, as described above.

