## 8.2. Dose Modification of Pembrolizumab

The toxicity of pembrolizumab could be accentuated by administration of NT-I7 and the component attributable to pembrolizumab and NT-I7 will be difficult if not impossible to sort out. Thus, the management of pembrolizumab will be used for the treatment of any AE. NT-I7 treatment will be discontinued when pembrolizumab must be **permanently discontinued**.

AEs associated with pembrolizumab exposure may represent an immune-related response. These irAEs may occur shortly after the first dose or several months after the last dose of pembrolizumab treatment and may affect more than one body system simultaneously. Therefore, early recognition and initiation of treatment is critical to reduce complications. Based on existing clinical study data, most irAEs were reversible and could be managed with interruptions of pembrolizumab, administration of corticosteroids and/or other supportive care. For suspected irAEs, ensure adequate evaluation to confirm etiology or exclude other causes. Dose modification and toxicity management guidelines for irAEs associated with pembrolizumab are provided in [Table 4](#).

When study interventions are administered in combination, attribution of an adverse event to a single component is likely to be difficult. Therefore, while the investigator may attribute a toxicity event to the combination, to NT-I7 alone, or to pembrolizumab alone, for adverse events listed in [Table 4](#), both interventions must be held according to the criteria in .

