**Table 4: Dose Modification and Toxicity Management Guidelines for Immune-related AEs Associated with Pembrolizumab**

General instructions: 
Severe and life-threatening irAEs should be treated with IV corticosteroids followed by oral steroids. Other systemic immunosuppressive treatment may be considered if the irAEs are not controlled by corticosteroids.
 
The corticosteroid taper should begin when the irAE is <math>\leq</math> Grade 1 and continue at least 4 weeks.
 
If pembrolizumab has been withheld, pembrolizumab may resume after the irAE decreased to <math>\leq</math> Grade 1 after corticosteroid taper.
 
If another episode of a severe adverse reaction occurs, permanently discontinue pembrolizumab.
				
irAEs	Toxicity grade (CTCAE V5.0)	Action with pembrolizumab	Corticosteroid and/or other therapies	Monitoring and follow-up
Pneumonitis	Grade 2	Withhold	Administer corticosteroids (initial dose of 1 to 2 mg/kg prednisone or equivalent) followed by taper	Monitor subjects for signs and symptoms of pneumonitis  Evaluate subjects with suspected pneumonitis with radiographic imaging and exclude other causes. Initiate corticosteroid treatment.
	Recurrent Grade 2, Grade 3 or 4	Permanently discontinue		
Colitis	Grade 2 or 3	Withhold	Administer corticosteroids (initial dose of 1 to 2 mg/kg	Monitor subjects for signs and symptoms of colitis and exclude other causes.

	Grade 4	Permanently discontinue	prednisone or equivalent) followed by taper	
Hepatitis	Grade 2	Withhold or discontinue based on severity of liver enzyme elevations.	Administer corticosteroids (initial dose of 0.5 to 1 mg/kg prednisone or equivalent) followed by taper	Monitor subjects for changes in liver function (at the start of treatment, periodically during treatment, and as indicated based on clinical evaluation) and symptoms of hepatitis and exclude other causes.
	Grade 3 or 4		Administer corticosteroids (initial dose of 1 to 2 mg/kg prednisone or equivalent) followed by taper	
Type 1 diabetes mellitus (T1DM) or Hyperglycemia	T1DM		Initiate insulin replacement therapy for subjects with T1DM	Monitor subjects for hyperglycemia or other signs and symptoms of diabetes

	Severe hyperglycemia	Withhold until metabolic control is achieved		

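### Section 6.4.1 makes stopping for recurrent Grade 2 pneumonitis discretionary, whereas Table 4 and Section 8.2 require both drugs to stop when the event is immune-related or treatment-related; no precedence is stated

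*Protocol*

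**What the plan says.** **Section 6.4.1, lead-in to the reasons for stopping.** "A subject may be discontinued from treatment but continue to be monitored in the trial for any of the following reasons".

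**Section 6.4.1, discretionary bullet.** "Discontinuation of treatment may be considered, at the discretion of the treating physician per criteria below, but continue to be monitored in the study". The first reason beneath it is "Recurrent Grade 2 pneumonitis", with no limit by cause or relatedness.

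**Section 6.4.1, later bullet.** "Any study intervention-related toxicity specified as a reason for permanent discontinuation" under the Section 8.2 guidelines is also listed as a reason. No order of priority is given between this bullet and the discretionary one.

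**Section 8.2, Table 4, pneumonitis rows.** A first Grade 2 episode means pembrolizumab is withheld. The row "Recurrent Grade 2, Grade 3 or 4" carries the action of permanent discontinuation.

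**Section 8.2, opening text.** Because the two drugs' toxicities are hard to separate, "the management of pembrolizumab will be used for the treatment of any AE". It adds that "NT-I7 treatment will be discontinued when pembrolizumab must be" permanently discontinued.

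**The concern.** Section 6.4.1 is where site staff would look for stopping rules, and the only pneumonitis event it names is in the item left to the treating physician. A reader can reasonably let a named item prevail over a general pointer to another section. A site doing so could regard further treatment as open for a subject whom Table 4 takes off both drugs.

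The protocol itself treats this toxicity as important. Section 4.2 excludes subjects with current pneumonitis, or with a history of non-infectious pneumonitis that needed steroids. Section 11.4 makes pneumonitis of any grade an event for expedited reporting. Section 8.2 warns that NT-I7 could accentuate pembrolizumab toxicity. Section 14.3 prohibits protocol waivers, so a site that followed the discretionary item would depart from Table 4 with no stated rule for classifying what it had done.

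**Working it through.** No arithmetic applies. The check sets the provisions for one event side by side and looks for a rule that reconciles them.

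| Provision | What it gives for recurrent Grade 2 pneumonitis |
|---|---|
| 6.4.1, discretionary bullet | Stopping may be considered by the treating physician |
| 6.4.1, later bullet | Refers to permanent stops in Section 8.2; no precedence stated |
| 8.2, Table 4 | Pembrolizumab permanently discontinued |
| 8.2, opening text | NT-I7 stops as a consequence |

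1. **Does Table 4 deliberately escalate on recurrence?** Yes. First-episode Grade 2 has its own row with a lesser action, and recurrent Grade 2 is grouped with Grades 3 and 4.

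2. **Does the later bullet in 6.4.1 settle the matter?** It softens the conflict. It does not resolve it, because it names no event and sets no priority over the item that does.

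3. **Does scope settle it?** In part. The note after Table 4 leaves events that are not immune-related to clinical practice, and Section 10 ties the treatment guidelines to events judged related to pembrolizumab. Pneumonitis outside Table 4 is therefore not in conflict. The discretionary item, however, is not limited to such cases, so the inconsistency remains for immune-related or treatment-related events.

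4. **Is there a precedence statement elsewhere?** None was found in Sections 6.5, 8.1, 8.1.1 or 10, or in the SAP.

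5. **What limits the practical risk?**
   - Section 8.2 holds both drugs for events listed in Table 4, whichever drug the investigator blames. Further dosing would therefore be a restart.
   - Section 8.2 allows a restart only when the toxicity has resolved and the conditions match Table 4. Otherwise the subject comes off all study treatment.
   - Section 8.1.1 requires drug-related pulmonary toxicity to return to baseline. Persistent Grade 1 pneumonitis is an exception only after a steroid taper of at least 1 month and with approval from the Medical Monitor and the Sponsor. Section 8.1.1 does not itself say that recurrence ends treatment.

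6. **Does it reach the statistics?** The sample size, alpha, power and ORR analysis take no input from this stopping rule.

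**The case against.** The strongest reply is that 6.4.1 is a catalogue of reasons and the operative rules are elsewhere. Pregnancy sits under the same permissive lead-in, yet Section 11.8 makes it an immediate stop. Confirmed progression sits there too, and Section 6.5 makes it a stop with an exception only after consulting the Sponsor. Section 6.1 sends readers to Sections 8.1 and 8.2 for dose modification. This much stands: the lead-in alone does not show real discretion. But the pneumonitis item carries its own discretion wording, which pregnancy and progression do not.

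A second reply offers a consistent reading. The later bullet covers toxicity related to study treatment, so the discretionary item would be left with unrelated pneumonitis. That is probably what a careful reader would conclude, but 6.4.1 does not say it.

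A third reply is that harm would require a site to act on one line and ignore Table 4 and both the hold and restart rules of Section 8.2. This largely stands, and it is why the point is minor.

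A reader might infer something stronger, namely that 6.4.1 instructs or authorises continued dosing against Table 4. The documents do not support that. Permission to consider stopping does not require continuing, and nothing in 6.4.1 authorises a restart. Nor should one count provisions on each side. Only the Table 4 row makes this event a permanent stop; the NT-I7 stop follows from it, and the restart rule is a conditional backstop for any toxicity.

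**Conclusion.** This is an internal inconsistency, wrong as written and minor. For immune-related or treatment-related recurrent Grade 2 pneumonitis, 6.4.1 leaves to judgement a stop that Table 4 and Section 8.2 require for both drugs, and 6.4.1 does not say which governs. It is a drafting fault in a safety rule; no design decision is in question.

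Its size is one named event. The documents give no frequency for it, so the number of subjects affected cannot be stated. They also do not show how many subjects remain on treatment; Section 2.3 describes the Arm IV and V cohorts as completed. The ORR analysis is not affected.

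The conclusion assumes that the pneumonitis item belongs to the discretionary sentence it directly follows. It does not otherwise depend on how the bullets are indented, which the extracted text does not show reliably.

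**What to change.** Make two edits in Section 6.4.1:

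1. Delete recurrent Grade 2 pneumonitis from the discretionary item.
2. Reword the later bullet along these lines: *Toxicities for which Section 8.2 or Table 4 specifies permanent discontinuation, including recurrent Grade 2 pneumonitis, must lead to discontinuation of both pembrolizumab and NT-I7. This takes precedence over any other provision of Section 6.4.1.*

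The deletion removes no discretion that is needed. Pneumonitis outside Table 4 stays under the general bullet for cases where the investigator believes, on safety or tolerability grounds, that "it is in the best interest of the subject to discontinue study drug". The other contents of the discretionary item, including the text on confirmed CR and on completing up to 35 treatments, can be left alone. Sections 8.1, 8.1.1 and 8.2 need no change.

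If any subject is still on treatment, send sites a short clarification letter. The cost is two wording changes and, where needed, that letter.
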